### 5.3.2. Blinding

Parts 1 and 2 of this study are double-blinded. Neither participants, nor investigators, nor the sponsor study team will be aware of treatment assignments prior to the final data base lock at the conclusion of the study.

Note: It is possible that some participants have SARS-CoV-2 negative result on the screening point of care test, but could be positive on the baseline SARS-CoV-2 PCR test. The results from the baseline test will not be available until after the participant is randomized. Once positive results are known from the baseline test, these participants will be unblinded and have the option to continue to be followed according to the Prevention Cohort SoA. Unblinded participants will not be included as part of the defined prevention population. [Table PYAD.5.1](#) describes general procedures for unblinding.

**Table PYAD.5.1. Unblinding Procedures for Study J2X-MC-PYAD(c)**

Unblinding (IWRS)	

Emergency unblinding for adverse events may be performed through the IWRS. All actions resulting in an unblinding event are recorded and reported by the IWRS

In case of an emergency, the investigator has the sole responsibility for determining if unblinding of a participants' intervention assignment is warranted

Participant safety must always be the first consideration in making such a determination. However, the investigator should make all attempts to contact the Medical Monitor in advance of unblinding

If a participant's intervention assignment is unblinded, the sponsor must be notified immediately after breaking the blind even if consultation occurred in advance

The date and reason that the blind was broken must be recorded in the source documentation and case report form

-------------------	--

Abbreviation: IWRS = interactive web-response system.

If an investigator, site personnel performing assessments, or participant is unblinded while the infusion is ongoing, the participant must be discontinued from the study intervention and the infusion stopped. If any amount of study intervention was administered, follow procedures according to the Schedule of Activities (SoA).

Part 3 is open label.

## 6. A Priori Statistical Methods

### 6.1. General Considerations

Statistical analysis of this study will be the responsibility of the sponsor or its designee.

All tables, figures, and listings will be created using the clinical trial database (unless otherwise noted), including data during study participation. While not reflected in a table, figure, or listing, any data collected after study participation (e.g., in the Lilly Safety System or collected through queries to the investigator) may be discussed in a clinical study report (CSR) or integrated summary document when deemed relevant.

Unless otherwise noted, displays will include columns for each treatment group, investigational product (IP) and another column for placebo will be displayed. A column that combines IP with placebo (i.e., a total column) will not be created.

Not all displays described in this statistical analysis plan (SAP) will necessarily be included in the CSR. Not all displays will necessarily be created as a “static” display. Some may be incorporated into interactive display tools instead of, or in addition to, a static display. Any display described in this SAP and not provided would be available upon request.

All statistical analyses will be performed using SAS software Version 9.4 (or a higher version), FACTS 6.0 (or a higher version), and/or R 3.6 (or a higher version).

#### 6.1.1. Analysis Populations

Patient populations are defined in [Table PYAD.6.1](#) along with the analysis they will be used to conduct. The treatment groups and inferential comparisons described in [Table PYAD.6.1](#) will be used unless otherwise specified. Also, unless otherwise specified, for all populations/analysis, patients will be analyzed according to the treatment to which they were assigned.

If enrolling to a placebo-controlled trial is challenged by an effective medication becoming available for prevention of COVID-19 and SARS-CoV-2, then the placebo arm may be dropped in Part 2.

Throughout the document, the term “the Prevention populations” will be used to describe both the Part 1 Prevention and Part 2 Prevention populations. Analyses on the Prevention populations will be conducted on each Prevention population separately. The terms “the Treatment populations” and “the Safety populations” are defined similarly, including those populations from Part 3 of the study.

Table PYAD.6.1. Analysis Populations

Population	Description
Entered	
Definition: All patients who signed informed consent.
 
Purpose: Used for disposition analysis.
 
Treatment Groups: None
 
Inferential Comparisons: None

Enrolled/Intent-to-Treat (ITT)	
Definition: All participants assigned to treatment, regardless of whether they take any doses of study treatment, or if they took the correct treatment. Patients will be analyzed according to the treatment group to which they were assigned.
 
Purpose: Used for disposition, demographic, and safety analyses.
 
Treatment Groups (Short Label):
 
 
Part 1: 4200 mg LY3819253 (4200 LY) and placebo (Pbo)
 
Part 2: 700 mg LY3819253, 350 mg LY3819253 + 700mg LY3832479, and placebo
 
 
Inferential Comparisons: LY versus placebo

Part 1 Prevention	
Definition: All participants in the Enrolled/Intent-to-Treat population in Part 1 who are SARS-CoV-2 RT-PCR negative and serology negative at baseline.
 
Purpose: Used for efficacy and health outcomes analyses.
 
Treatment Groups (Short Label): 4200 mg LY3819253 (4200 LY) and placebo (Pbo)
 
Inferential Comparisons: LY versus placebo

Part 2 Prevention	
Definition: All participants in the Enrolled/Intent-to-Treat population in the Prevention Cohort in Part 2 who are SARS-CoV-2 RT-PCR negative and serology negative at baseline.
 
Purpose: Used for efficacy and health outcomes analyses.
 
Treatment Groups (Short Label): 700 mg LY3819253, 350 mg LY3819253 + 700mg LY3832479, and placebo
 
Inferential Comparisons: LY3819253 versus placebo, LY3819253 + LY3832479 versus placebo

Part 1 Treatment	
Definition: All participants in the Enrolled/Intent-to-Treat population in Part 1 who are SARS-CoV-2 RT-PCR positive at baseline and serology negative at baseline.
 
Purpose: Used for efficacy and health outcomes analyses.
 
Treatment Groups (Short Label): 4200 mg LY3819253 (4200 LY) and placebo (Pbo)
 
Inferential Comparisons: LY versus placebo

Part 2 Treatment	
Definition: All participants in the Enrolled/Intent-to-Treat population in the Treatment Cohort in Part 2 who are POC positive, RT-PCR positive, and SARS-CoV-2 serology negative at baseline.
 
Purpose: Used for efficacy and health outcomes analyses.
 
Treatment Groups (Short Label): 700 mg LY3819253, 350 mg LY3819253 + 700mg LY3832479, and placebo
 
Inferential Comparisons: LY3819253 versus placebo, LY3819253 + LY3832479 versus placebo

Part 3 Treatment	
Definition: All participants in the Enrolled/Intent-to-Treat population in Part 3 who are RT-PCR positive, and SARS-CoV-2 serology negative at baseline.
 
Purpose: Used for efficacy and health outcomes analyses.
 
Treatment Groups (Short Label): 700 mg LY3819253 and 700 mg LY3819253 + 1400mg LY3832479
 
Inferential Comparisons: LY3819253 versus LY3819253 + LY3832479 (not powered for formal inference)

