9.4. Statistical Analyses

Statistical analysis of this study will be the responsibility of Sponsor or its designee.

All tests of treatment effects will be conducted at a 2-sided alpha level of 0.05, unless otherwise stated, and all confidence intervals will be given at a 2-sided 95% level.

For subgroup analyses, all tests of interactions between treatment groups and other factors will be conducted at a 2-sided alpha level of 0.10.

Any change to the data analysis methods described in the protocol will require an amendment only if it changes a principal feature of the protocol. Any other change to the data analysis methods described in the protocol, and the justification for making the change, will be described in the statistical analysis plan (SAP) and the clinical study report (CSR). Additional exploratory analyses of the data will be conducted as deemed appropriate.

The statistical analysis plan will be finalized prior to un-blinding and it will include a more technical and detailed description of the statistical analyses described in this section. This section is a summary of the planned statistical analyses of the most important endpoints including primary and key secondary endpoints.

For analyses on the Part 2 Prevention population, LY3819253 700 mg and LY3819253 350 mg + LY3832479 700 mg will be assessed against placebo separately.

For analyses on the Part 3 Treatment population, results will be summarized separately for LY3819253 700 mg and LY3819253 700 mg + LY3832479 1400 mg. Part 3 is not powered for inference between the two treatment arms.

If enrolling to a placebo-controlled trial is challenged by an effective medication becoming available for prevention of COVID-19 and SARS-CoV-2, then the placebo arm may be dropped.

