## **5.2. Determination of Sample Size**

For Part 1, an estimated 33 events are needed to show superiority of LY3819253-4200mg over placebo in each of the primary and key secondary endpoints, using the formula by Schoenfeld (1983). An average sample size of approximately 1300 participants who are SARS-CoV-2 PCR negative and serology negative at baseline is expected to obtain the needed number of events for each endpoint.

For Part 2, an estimated 56 events in the Prevention Cohort are needed to show superiority over placebo for either LY3819253-700mg or LY3819253-350mg+LY3832479-700mg in each of the primary and key secondary endpoints. Approximately 2000 participants on average will be randomly assigned to study intervention such that approximately 1700 participants are randomized in the Prevention Cohort with the goal of achieving approximately 56 events on each of the primary and key secondary endpoints.

The maximum sample size for this study is approximately 5000 participants in the intent-to-treat (ITT) population.

Participants will be residents and staff of skilled nursing and assisted living facilities. Globally, there are many reports of the rapid spread of COVID-19 amongst residents of skilled nursing facilities following identification of an index case, with high associated rates of morbidity and mortality (Arons et al. 2020; Grabowski). Given that residents at these facilities are at higher risk for having a more severe disease course of COVID-19, this will be an important population to participate in the study. Therefore, a minimum of 300 residents will be enrolled.

Operationally, this will be accomplished, when possible, by identifying facilities where approximately half of the participants interested in the study are residents.

For sample size determination for Part 1, the following assumptions were used:

- 1) two-sided significance level of 0.05;
- 2) 90% power for the primary and key secondary endpoints;
- 3) an 8-week placebo group event rate of 4.0% for moderate or worse severity COVID-19;
- 4) a risk ratio of 0.33 between LY3819253 and placebo in terms of the primary and key secondary endpoints.

For sample size determination for Part 2, the following assumptions were used:

- 1) two-sided significance level of 0.025;
- 2) 90% power for the primary and key secondary endpoints;
- 3) an 8-week placebo group event rate of 5.3% for moderate or worse severity COVID-19;

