#### **6.1.5.2. Part 2 Primary Analysis**

Database lock for the primary and key secondary endpoints in Part 2 (the Part 2 Primary Database Lock) will be triggered when 56 participants in the Part 2 Prevention population experience a moderate or worse severity case of COVID-19. All pre-specified analyses for participants in Part 2 will be based on the Part 2 Primary Database Lock.

To account for participants who have not finished the Evaluation Period at the time of the Primary Database Lock, a supplementary database lock (the Part 2 End of Evaluation Database Lock) will occur once all participants have completed the Evaluation Period or discontinued from the study. The analyses conducted during the Primary Database Lock will be re-evaluated at the End of Evaluation Database Lock.

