#### **6.10.2.2. Risk Difference/Time-to-Event Assessment**

The risk difference for COVID-19 between treatments will be estimated by the difference in the percentages of patients in the Prevention population who experience COVID-19 by Day 57, unadjusted for other covariates. A Wald 95% confidence interval for the risk difference will be computed.

The time from randomization to first incidence of COVID-19 will be summarized by treatment for participants within the Prevention population. A 95% confidence interval for the hazard ratio will be computed using a Cox proportional hazards model. Participants who have yet to complete the Evaluation Period at the time of the analysis will be censored at the date of their last visit prior to the analysis.

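### If the Part 2 placebo arm is dropped, nothing limits the placebo comparisons or the 56-event count to concurrently randomized participants; the crude, Cox and random-facility analyses are exposed, the confirmatory tests largely are not

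*SAP*

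**What the plan says.** Both documents authorise the drop: "then the placebo arm may be dropped" (Protocol 9.4) and "then the placebo arm may be dropped in Part 2" (SAP 6.1.1). The condition is that an effective medication for prevention becomes available and makes placebo-controlled enrolment hard to sustain.

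The analysis rules do not change with it:

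- **Population.** SAP 6.1.1 defines Part 2 Prevention as everyone randomized "in the Prevention Cohort in Part 2 who are SARS-CoV-2 RT-PCR negative and serology negative at baseline". The listed comparisons are "LY3819253 versus placebo, LY3819253 + LY3832479 versus placebo". Protocol 9.4 likewise says that "LY3819253 700 mg and LY3819253 350 mg + LY3832479 700 mg will be assessed against placebo separately".
- **Lock.** SAP 6.1.5.2 sets the condition for the main Part 2 lock: it "will be triggered when 56 participants in the Part 2 Prevention population experience a moderate or worse severity case of COVID-19". SAP 5.2 gives the origin of the number: "an estimated 56 events in the Prevention Cohort are needed to show superiority over placebo".
- **Primary and key secondary tests.** SAP 6.10.1 uses logistic regression with treatment, facility, role and sex as fixed effects. SAP 6.10.3.1 and 6.10.3.2 use the same method.
- **Other analyses of the primary outcome.** SAP 6.10.2.1 fits facility as a random effect. SAP 6.10.2.2 takes the difference in the percentages of patients "who experience COVID-19 by Day 57, unadjusted for other covariates", and adds a Cox hazard ratio for which it names no covariates. Protocol 9.4.1 lists treatment alone for Cox models.

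I found no text in either document that limits these comparisons to participants randomized while placebo was open, adjusts for calendar time, or revises the trigger after a drop.

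**The concern.** Participants randomized after a drop have no placebo group enrolled alongside them. Any analysis that pools them with earlier active participants and sets the total against the earlier placebo group mixes the drug effect with whatever happened to infection risk over time. The drop condition makes such a change plausible, since it requires that a new preventive has become available.

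The trigger raises a second issue. Cases among post-drop participants count toward 56 but carry no direct information on drug versus placebo. A lock reported as reached at 56 events would then suggest more placebo-controlled information than exists.

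**Working it through.** **Inputs from the documents.** About 1700 in the Part 2 Prevention Cohort; 56 events; placebo rate 5.3% at 8 weeks for moderate-or-worse COVID-19; risk ratio 0.33; 90% power; two-sided 0.025 for sizing (SAP 5.2); allocation 1:1:1 (Protocol 6.3). **Assumptions:** the timing of the drop, the change in background incidence, and equal allocation to the two active arms afterwards.

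**1. The plan's 56 events.** Schoenfeld's formula for a 1:1 pair is d = 4(z₁ + z₂)² / (ln h)². A risk ratio of 0.33 at 5.3% is an odds ratio of (0.01749/0.98251) / (0.053/0.947) = 0.318. Then d = 4(2.241 + 1.282)² / (ln 0.318)² = 37.8 per pair, and 37.8 × 3/2 = 56.8 for three arms, close to the stated 56. The 3/2 step is my assumption, because the documents do not show how the total was formed. The same route gives 32.6, so 33, for Part 1, as stated.

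**2. Crude contrast with an inert drug.** Drop at half of 1700: 850/3 = 283 per arm before, 850/2 = 425 per active arm after. An active arm is therefore 283/708 = 40% concurrent and 60% post-drop. If background incidence is multiplied by k after the drop, the expected crude risk ratio is 0.4 + 0.6k.

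| Drop at | k = 0.5 | k = 2 |
|---|---|---|
| 50% | 0.70 | 1.60 |
| 75% (weights 2/3, 1/3) | 0.83 | 1.33 |

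The ratio does not depend on the base rate. At 5.3%, the 50% row means 3.71% or 8.48% in the active arm, a risk difference of −1.59 or +3.18 percentage points from a drug that does nothing. The 5.3% is the moderate-or-worse rate; the documents give none for the primary endpoint.

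**3. Does the facility term help?** A simulation with an inert drug assumed 1700 participants, 24 per facility, between-facility log-SD 0.8, and every facility wholly before or wholly after the drop. For a 50% drop, a nominal 5% crude two-proportion test rejected about 22% of the time with incidence halved (nearly all favouring drug) and about 40% with it doubled (all against drug). A facility-stratified score test, standing in for the fixed-facility logistic test, stayed at about 5% in every scenario. A facility without placebo adds nothing direct to the contrast. The random-facility model was not simulated; it is exposed because it uses between-facility comparisons.

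**4. Events at the lock.** Expected events per participant are 0.053 × (1 + 0.33 + 0.33)/3 = 0.02933 before the drop and 0.053 × 0.33 = 0.01749 after. If a fraction f of final enrolment precedes the drop, N = 56 / [0.02933f + 0.01749(1 − f)]. Concurrent events per active-placebo pair are the concurrent total × 1.33/1.66.

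| Drop at | N at 56 events | Concurrent | Without concurrent placebo | Concurrent per pair | Power at 0.025 | Power at 0.05 |
|---|---|---|---|---|---|---|
| none | 1910 | 56 | 0 | 44.9 | 93–94% | 96–97% |
| 75% | 2124 | 46.7 | 9.3 | 37.4 | 88–90% | 92–94% |
| 50% | 2392 | 35.1 | 20.9 | 28.1 | 76–79% | 84–86% |

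Power ranges run from effect size 0.33 to 0.318 and refer to the moderate-or-worse endpoint. The primary endpoint also includes mild cases, so its event count would be at least as large.

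**The case against.** **The confirmatory tests do not inherit the crude bias.** This stands. A reader might infer from the population definition that the alpha-bearing results are distorted. The documents do not support that. Both key secondary endpoints share the fixed-facility model, randomization is blocked within facility (Protocol 6.3), and screening through dosing must finish within 7 days of the index case (SAP 5.1.1), so few facilities could straddle a drop. The exposed analyses carry no alpha in SAP 6.5.

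**The incidence scenarios are assumed.** This also stands. A new preventive makes a fall plausible, but it does not explain a doubling; that case stands for an epidemic wave. Vaccination also has limited direct reach: vaccinated people are excluded from Part 2 (Protocol 5.2), and vaccine use is to wait until Week 8 (Protocol 6.5). Infection pressure around participants could still change.

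**The trigger does not cause the information loss.** This largely stands. Once placebo closes, concurrent events are capped whatever is counted. SAP 6.1.5.2 also plans a re-analysis at the End of Evaluation Database Lock. What remains is that the primary lock may wait for events that say nothing direct about placebo, and 56 would misdescribe the information reached.

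**The drop is optional.** True, but both documents pre-authorise it, so its analysis should be pre-specified too.

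**Conclusion.** The gap is real and specific. If placebo is dropped and the SAP is followed as written, the by-arm percentages, unadjusted risk difference, Cox hazard ratio and random-facility model would include participants with no concurrent placebo. With an inert drug and a halfway drop, the crude risk ratio would be expected at 0.70 or 1.60 under assumed halving or doubling of incidence. The primary and key secondary tests are largely protected.

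At the plan's own rates and constant incidence, about 21 (50% drop) or 9 (75% drop) of the 56 triggering events would lack concurrent placebo.

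Two stronger readings should be avoided:

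- A reader might compute 31 or 19 non-concurrent events by fixing the drop at 850 or 1275 of the planned 1700. Those counts need enrolment to continue to about 2,630 or 2,340. With 1700 participants and a halfway drop, only 850 × 0.02933 + 850 × 0.01749 = 24.9 + 14.9 = 39.8 events are expected, and the trigger is not reached.
- A reader might extend the bias to the safety comparisons. Expected COVID-19 signs, symptoms and progression are generally not recorded as adverse events (Protocol 8.1.2 and 10.3.1), so changing COVID-19 incidence largely does not carry over, and no size can be given.

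The sponsor should make the change while it can still precede any drop, but the point does not threaten the primary test.

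**What to change.** Add to SAP 6.1.1, 6.1.4 and 6.10.2: if the Part 2 placebo arm is dropped, all comparisons with placebo are restricted to participants randomized while that arm was open. Later participants are summarized descriptively or used only to compare the active arms with each other.

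In SAP 6.1.5.2, count trigger events in the concurrent set only. Lock at 56 such events or when all concurrently randomized participants have completed Day 57 or discontinued, whichever is first, and report the concurrent event count actually reached. The fallback is necessary because 56 concurrent events may become unreachable after a drop, and it would usually be what applies.

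The cost is SAP wording and one randomization-period flag in the data. Post-drop active participants would add no precision to the placebo contrast. The change keeps that contrast concurrent and avoids waiting for uninformative events; it cannot recover power lost by dropping placebo.

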## Analysis Populations

Population	Description
Part 1 Safety	
Definition: All participants randomly assigned and who received any amount of study intervention in Part 1. Participants will be analyzed according to the intervention they actually received.
 
Purpose: Used for safety analyses.
 
Treatment Groups (Short Label): 4200 mg LY3819253 (4200 LY) and placebo (Pbo)
 
Inferential Comparisons: LY versus placebo

Part 2 Safety	
Definition: All participants randomly assigned and who received any amount of study intervention in Part 2. Participants will be analyzed according to the intervention they actually received.
 
Purpose: Used for safety analyses.
 
Treatment Groups (Short Label): 700 mg LY3819253, 350 mg LY3819253 + 700mg LY3832479, and placebo
 
Inferential Comparisons: LY3819253 versus placebo, LY3819253 + LY3832479 versus placebo

Part 3 Safety	
Definition: All participants randomly assigned and who received any amount of study intervention in Part 3. Participants will be analyzed according to the intervention they actually received.
 
Purpose: Used for safety analyses.
 
Treatment Groups (Short Label): 700 mg LY3819253 and 700 mg LY3819253 + 1400mg LY3832479
 
Inferential Comparisons: LY3819253 versus LY3819253 + LY3832479 (not powered for formal inference)

Fully Dosed	
Definition: All participants in the Safety population who receive either placebo or a complete infusion of study intervention.
 
Purpose: Used for sensitivity assessments in the event that there are patients who do not receive a complete infusion of study drug.
 
Treatment Groups (Short Label): Part 1: 4200 mg LY3819253 (4200 LY) and placebo (Pbo)
 
Part 2: 700 mg LY3819253, 350 mg LY3819253 + 700mg LY3832479, and placebo
 
Inferential Comparisons: LY versus placebo

Pharmacokinetic	
Definition: All randomized participants who received study intervention and have at least 1 postdose PK sample. Participants will be analyzed according to the intervention they received.
 
Purpose: Used for PK analyses.
 
Treatment Groups (Short Label):
 
Part 1: 4200 mg LY3819253 (4200 LY) and placebo (Pbo)
 
Part 2: 700 mg LY3819253, 350 mg LY3819253 + 700mg LY3832479, and placebo
 
Inferential Comparisons: LY versus placebo

Abbreviations: ITT = intent to treat; RT-PCR = reverse transcription – polymerase chain reaction; PK = pharmacokinetic; SARS-CoV-2 = severe acute respiratory syndrome coronavirus 2.

